6.2 Analysis methods

6.2.1 Primary analysis

The primary analysis will be done according to the FAS (ITT) and PP sets specified in section 4.2, using the adjusted model (4, 5). The randomization group will be used as the main predictor, adjusting for the stratification factors and relevant predefined covariates. To account for the fact that participants are clustered in PCP practices, we will use bootstrapped standard errors (1000 reps). A random seed will be predefined for replicability. The intraclass coefficient is expected to be small. All effects will be shown using marginal point estimates (accounting for adjustment variables) and 95% confidence intervals.

For the first co-primary endpoint, reduction in ABSS, we will use a linear regression, e.g.:

bootstrap, reps(1000) seed(XXX): regress y x1 x2

This endpoint should be normally distributed, as observed in previous studies (3). However, if it is not normally distributed, we will use a log-transformation after adding the constant 1.

For the second co-primary endpoint, *proportion of antibiotics use*, we will use a logistic regression, e.g.:

bootstrap, reps(1000) seed(xxx): glm y x1 x2, fam(bin) link(log) eform

We will use multiple imputation to handle missing values on covariates and outcomes (see section 6.4). If there is collinearity between covariates, we will remove one collinear variable based on theoretical reasons.

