2.1 Trial design

This is a pragmatic, open-label, superiority randomized controlled trial, which takes place in ~40 PCP in practices and 5 walk-in clinics. The intervention group receives Kaloba® for 7 days and up to 21 days. The control group receives usual care, with symptomatic treatments freely chosen by the PCP (phytotherapy excluded). Usual care is not standardized between PCPs. A delayed use of antibiotics can be used in both groups. Prescription of paracetamol is allowed, as well as any routine medication pre-reviewed by the PCP and not counter-indicated.

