2.2 Randomization

Participants are randomized in a 1:1 ratio to either the intervention group or the control group, with stratification according to PCP. Randomization was performed using blocks of equal size (size=4). An independent statistician built the randomization table.

Study group allocation is done using the web-based system REDCap (hosted by the University of Fribourg), which also contains the electronic case report form (eCRF). The PCP uses the button "randomize" in REDCap to allocate each patient to a group.

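### PCP is the randomisation stratum, but the co-primary models do not list it and the bootstrap's resampling unit is not named

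*Combined protocol and SAP*

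**What the plan says.** Section 2.2 randomises patients 1:1 in blocks of 4, "with stratification according to PCP". Section 2.1 puts the trial in about "40 PCP in practices and 5 walk-in clinics" and notes that "Usual care is not standardized between PCPs".

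Section 6.2.1 says that the primary models estimate the group effect while "adjusting for the stratification factors and relevant predefined covariates". It then deals with clustering: "To account for the fact that participants are clustered in PCP practices, we will use bootstrapped standard errors (1000 reps"). It adds that "The intraclass coefficient is expected to be small", without a value.

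The covariates are listed under estimand E1.1 in section 4.3, and E2.1 takes over the same list. One model has type of recruitment alone. The other adds patient characteristics: age, sex, education, smoking, symptom duration, baseline ABSS and corticosteroid prescriptions. PCP is in neither. The fallback for too few participants under E2.1 also keeps only type of recruitment at site level.

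The two example commands in section 6.2.1 use placeholder covariates and have no cluster or strata option. Section 2.2 does not say what the stratum was in the walk-in clinics.

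**The concern.** Two statements cannot both be followed. An analyst who adjusts for the stratification factor must include PCP; one who follows the list in section 4.3 must leave it out. Type of recruitment is a two-level grouping of roughly 45 sites and cannot stand in for PCP.

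The clustering remedy is also incomplete. A bootstrap reflects PCP clustering only if whole PCPs are resampled, or if PCP is in the model and the effect is common to all PCPs. Resampling patients with no PCP term does neither.

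At stake are the SE, and so the test at 2.5%, for both co-primary outcomes. As things stand, the model and the resampling unit could be chosen after the data are seen.

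**Working it through.** **Inputs from the SAP.** N = 420; two-sided alpha 0.025; difference 1 day with SD 3; antibiotics 60% v 45% (section 2.3). About 45 sites (section 2.1). Blocks of 4 within PCP (section 2.2).

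**Assumptions.** One stratum per walk-in clinic; ICC 0.01 to 0.20, meaning the residual ICC after covariates; SD of the treatment effect between PCPs 0, 0.5 or 1 day; site sizes even or uneven. The SAP gives none of these.

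**Sample size.** The planned figures reproduce: 173 per group for days (noncentral t) and 210 per group for antibiotics (pooled variance, no continuity correction).

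**What the printed commands do.** With 1,000 replicates, patient resampling and no PCP term, the bootstrap SE was 0.998-0.999 times the independent-data SE. For days that SE is sqrt(4 x 9/420) = sqrt(0.0857) = 0.293.

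**Case A: effect common to all PCPs.** Blocking within PCP removes most between-PCP variance from the treatment comparison (about 0.911 of it, since some blocks are incomplete). The patient-level SE does not credit this. Reported SE / true SE = 1/sqrt(1 - 0.911 x ICC):

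| ICC | SE ratio | Type I error, simulated | Power for days: PCP omitted v random intercept |
|---|---|---|---|
| 0.01 | 1.005 | 2.7-2.9% | 88 v 88% |
| 0.05 | 1.024 | 2.1-2.2% | 89 v 90% |
| 0.10 | 1.049 | 2.0-2.2% | 89 v 91% |
| 0.20 | 1.106 | 1.3-1.5% | 90-91 v 94-95% |

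Monte Carlo error on the type I figures is about 0.22 points. For antibiotics at the same ICCs (uneven sites), power was 82 v 82%, 82 v 83%, 81 v 83% and 85 v 90%.

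**Case B: effect varies between PCPs, and the PCPs are a sample from a wider population.** Let S be the sum of squared site shares: 0.0247 (even) or 0.0460 (uneven).

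- True variance = 0.0857 x (1 - 0.911 x ICC) + SD² x S
- Reported variance = 0.0857 + SD² x 2/420

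Example at ICC 0.05, SD 1 day, uneven sites: true 0.0818 + 0.0460 = 0.1278; reported 0.0857 + 0.0048 = 0.0905; SE ratio sqrt(0.0905/0.1278) = 0.841. The critical value 2.241 then acts as 2.241 x 0.841 = 1.886, a two-sided rejection rate of 5.9%.

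| ICC | Effect SD (days) | SE ratio, even / uneven | Type I error by formula | Simulated |
|---|---|---|---|---|
| 0.01 | 0.5 | 0.977 / 0.949 | 2.9 / 3.3% | 2.7-3.7% |
| 0.05 | 0.5 | 0.994 / 0.965 | 2.6 / 3.1% | 2.9-3.5% |
| 0.01 | 1 | 0.908 / 0.831 | 4.2 / 6.2% | 4.6-6.4% |
| 0.05 | 1 | 0.922 / 0.841 | 3.9 / 5.9% | 4.1-6.3% |

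Separate simulations with other site-size patterns or simpler models gave 3.7-6.9% at SD 1 day. Setting the two variances equal gives the effect SD at which the errors cancel: 0.14-0.20 day at ICC 0.01 and 0.31-0.44 day at ICC 0.05.

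**Case C: effect varies, but the target is the average over the participating PCPs.** With PCP effects held fixed and their patient-weighted mean at zero, rejection was 1.9-2.5% at SD 0.5-1 day and ICC 0.01-0.05. There is no inflation.

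**What each remedy does in case B.** PCP in the model with its model SE still gave 2.7-3.8% at SD 0.5 day and 4.4-7.7% at 1 day. A PCP-clustered robust SE with a t reference gave 2.2-2.9% (even) and 2.8-3.4% (uneven) over all settings, common effects included. A PCP-level bootstrap with a t reference gave 2.5-3.0% and 2.8-3.5%; with a normal reference, 2.9-3.6% and 3.3-4.2%. A random treatment slope at SD 1 day and ICC 0.05 gave 2.6% and 2.3% in about 700 trials each (Monte Carlo error about 0.6 points).

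**Limits.** The main simulations used treatment, recruitment type and one baseline covariate, not the full list. The log-link antibiotics model was represented by Poisson regression with a robust SE.

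**The case against.** The commands are labelled as examples and use placeholders. The stated purpose of the bootstrap is to handle PCP clustering, which points towards resampling PCPs. If that is what is meant, the SE was within about 4% of the truth in every scenario of an independent check (ratio 0.96 to 1.02). This stands: the documents show an ambiguity, not a proven error in the SE. But neither the text nor the commands name the unit, so the ambiguity remains.

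The SAP also expects a small ICC. At 0.01-0.05 the common-effect error is conservative and costs at most about 1 point of power. This stands too, though a small ICC gives no protection against varying effects.

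A reader might infer that the plan understates uncertainty and inflates type I error. The documents do not support that. It requires three things together: patient resampling, a treatment effect that truly varies between PCPs, and PCPs treated as a sample from a wider population. No estimand in section 4.3 for a co-primary outcome names such a population. Unstandardised usual care makes variation possible but says nothing of its size, and clear inflation needs an effect SD about as large as the whole planned difference of 1 day.

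Nor should clustering be taken as a reason to enlarge the trial. Patients are randomised within PCP, so a common effect is estimated slightly more precisely than the independent-data formula assumes.

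**Conclusion.** The point holds as a gap in specification, of minor severity. Sections 2.2 and 6.2.1 call for PCP in the co-primary models and section 4.3 leaves it out; section 6.2.1 claims to handle clustering without naming what is resampled.

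The consequences are conditional. With patients resampled and PCP omitted, a common effect gives an SE about 0.5% too wide at ICC 0.01, 2.4% at 0.05, 5% at 0.10 and 11% at 0.20. With effects that vary between PCPs drawn from a wider population, type I error at ICC 0.01-0.05 is about 3-4% at effect SD 0.5 day and 4-7% at 1 day. With the participating PCPs as the target, there is no inflation. All ICCs, effect SDs and site-size patterns are assumptions.

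**What to change.** Reconcile sections 2.2, 4.3 and 6.2.1 before database lock.

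1. Include PCP in both co-primary models and keep the listed covariates. A random intercept serves both outcomes; absorbed PCP strata are an alternative for days. PCP dummies are not practical for antibiotics: in 76-100% of simulated null trials at least one PCP had all or none of its patients on antibiotics. State what the stratum was in the walk-in clinics.
2. State the target effect and the SE that goes with it. Either name PCP as the bootstrap resampling unit (or use a PCP-clustered robust SE), with a t reference on the number of PCPs minus 1. Or state that the target is a common effect, or the effect in the participating PCPs, and use the model SE with PCP in the model. A random treatment slope is another valid way to allow for varying effects. A PCP term with its model SE does not cover the wider-population target.

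Cost: no new data, since PCP is already recorded for randomisation, and N stays at 420. Clustered SEs cost about 1-2 points of power for days and 1-4 for antibiotics, and are slightly liberal with uneven sites (about 3% against 2.5%). Under absorbed strata, sites with patients in only one arm carry no information on the treatment effect (about 5 of 45 in the uneven scenario); a random intercept avoids most of that loss.

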4.3 Estimands

We define the following estimands for the outcomes.

Estimand E1.1: This estimand quantifies the effectiveness of the treatment assessed with the reduction of symptom severity (co-primary outcome).

Outcome of interest: Number of days needed to achieve a 50% reduction on the Acute Bronchitis Severity Score (ABSS) after peak of symptoms, assessed at max. 22 days. The peak of symptoms is defined by the highest ABSS (or the initial score if there is no peak). This is a normally distributed count outcome (3).

Population-level summary measure of outcome: adjusted* mean difference.

Participant-set of interest: FAS.

Handling of intercurrent events: All participants are included.

Handling of missing data: Missing data will be multiple imputed (see section 6.4).

* 1) Adjusted for the type of recruitment (PCP/walk-in clinic) and 2) adjusted for the following factors at baseline: type of recruitment, age, sex, level of education, smoking status, beginning of symptoms (number of days), baseline ABSS, and prescriptions for corticosteroid containing oral medication or inhalers (yes/no), including Prednisone, Symbicort, and Vannair.

Estimand E1.2: This estimand quantifies the effectiveness of the treatment assessed with the reduction of symptom severity (co-primary outcome) in the PP population.

Outcome of interest: Same as estimand 1.1.

Population-level summary measure of outcome: same as estimand 1.1.

Participant-set of interest: PP.

Handling of intercurrent events: Participants with ICE1-3 are excluded from the analysis. The data will be weighted according to inverse probability weighting for ICE 1 and 2 (see section 6.2.2).

Handling of missing data: As ICE cannot be assessed in participants who drop out or are lost to follow-up, we will not use multiple imputation. We will use inverse probability of attrition weights to account for attrition and multiple imputation for missing baseline covariates (see section 6.4).

SAP for PHYTOBRONCH	Version of SAP: 1	
Based on template: CTU_STA_TEM-11; v5.0.0	Valid from: 20.03.2025	Page 8 of 15

Estimand E2.1: This estimand quantifies the efficacy of the treatment assessed with the proportion of antibiotics use (co-primary outcome).

Outcome of interest: Use of antibiotics after the initial visit (binary).

Population-level summary measure of outcome: adjusted* risk ratio.

Participant-set of interest: FAS.

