Handling of intercurrent events: All participants are included. Participants who took antibiotics at baseline will be considered as failures (having antibiotics).

Handling of missing data: Missing data will be multiple imputed (see section 6.4).

* Same adjustment as E1.1. If there are too few participants, we will use analyses adjusting separately for each covariate + type of recruitment.

Estimand E2.2: This estimand quantifies the efficacy of the treatment assessed with the proportion of antibiotics use (co-primary outcome) in the PP population.

Outcome of interest: same as estimand 2.1.

Population-level summary measure of outcome: same as estimand 2.1.

Participant-set of interest: PP.

Handling of intercurrent events: Participants with ICE1-3 are excluded from the analysis. The data will be weighted according to inverse probability weighting for ICE 1 and 2 (see section 6.2.2).

Handling of missing data: As ICE cannot be assessed in participants who drop out or are lost to follow-up, we will not use multiple imputation. We will use inverse probability of attrition weights to account for attrition and multiple imputation for missing baseline covariates (see section 6.4).

Estimand E3.1: This estimand quantifies the incidence of AEs and SAEs.

Outcome of interest: Presence of any adverse or severe adverse event (binary) during the follow-up (up to 22 days).

Population-level summary measure of outcome: adjusted^{*} hazard ratio.

Participant-set of interest: SAF.

Handling of intercurrent events: All participants are included.

Handling of missing data: No missing data, participants are censored when the study ends (at day 22) or at the day of last contact.

* 1) Adjusted for the type of recruitment (PCP/walk-in clinic) and 2) adjusted for the following factors at baseline: type of recruitment, age, sex, level of education, smoking status, beginning of symptoms (number of days), and baseline ABSS. If there are too few participants, we will use analyses adjusting separately for each covariate + type of recruitment.

Estimand E3.2: This estimand quantifies the incidence of AEs and SAEs.

Outcome of interest: same as estimand 3.1.

Population-level summary measure of outcome: same as estimand 3.1.

Participant-set of interest: SAF without ICE2.

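### Section 6.2.1 calls the antibiotic-use model logistic but codes a log-binomial model. With the full covariate set at the planned rates, that model often has no interior maximum, and no fallback is named.

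*Combined protocol and SAP*

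**What the plan says.** SAP Section 6.2.1 introduces the model for antibiotic use with "we will use a logistic regression, e.g" and then gives the command "glm y x1 x2, fam(bin) link(log) eform". A binomial family with a log link is a log-binomial model, and its exponentiated coefficients are risk ratios. The estimand in Section 4.3 (E2.1) is stated as "Population-level summary measure of outcome: adjusted* risk ratio".

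Section 6.2.1 bases the primary analysis on the adjusted model, "adjusting for the stratification factors and relevant predefined covariates". E2.1 takes its adjustment from E1.1, which lists two levels: "1) Adjusted for the type of recruitment (PCP/walk-in clinic) and 2) adjusted for the following factors at baseline". The second level adds age, sex, education, smoking, symptom duration, baseline ABSS and corticosteroid prescription. On reporting, Section 6.2.1 says "All effects will be shown using marginal point estimates (accounting for adjustment variables) and 95% confidence intervals".

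The only fallback specific to this endpoint is in E2.1: "Same adjustment as E1.1. If there are too few participants, we will use analyses adjusting separately for each covariate + type of recruitment". Section 6.2.1 also allows a covariate to be dropped for collinearity. The alternative models in Sections 6.2.1 and 6.2.3 concern the ABSS endpoint. Section 6.2.6 points back to alternatives already described, but none is described for antibiotic use. Section 6.2.2 reuses the same model for the per-protocol set.

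**The concern.** There are two problems. First, the named model and the coded model differ. Exponentiated logistic coefficients are odds ratios, whereas E2.1 asks for a risk ratio. At the planned rates the two measures are far apart.

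Second, a log-binomial model is valid only while every fitted risk stays below 1. With risks near one half and three continuous covariates (age, symptom days, baseline ABSS), that limit can bind. The likelihood is then highest where some fitted risk equals 1. A finite boundary estimate exists under constrained maximum likelihood, but the command specifies no constrained fit. An unconstrained routine may fail, stop short of that estimate, or return fitted risks of 1 or more.

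The co-primary risk ratio could then depend on how the software treats the boundary. The SAP does not settle this, so in an open-label trial (Section 2.8) the choice may be made after the data are seen.

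**Working it through.** **Planned figures (Section 2.3).** Control 60%, intervention 45%, two-sided 2.5% level, power 80%. The pooled-variance formula is

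n = [z₀.₉₈₇₅·√(2p̄(1−p̄)) + z₀.₈₀·√(p₁q₁+p₂q₂)]² / (p₁−p₂)²

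With p̄ = 0.525 this is (2.2414·0.7062 + 0.8416·0.6982)² / 0.15² = 209.4, so 210 per group and 420 in total. The plan's figure is reproduced (power 80.1%).

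**The two measures.** Risk ratio = 0.45/0.60 = 0.75. Odds ratio = (0.45/0.55)/(0.60/0.40) = 0.545.

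**Coefficients in the full model (E1.1, second level; three education levels from Section 5.3).** Intercept 1, group 1, recruitment 1, age 1, sex 1, education 2, smoking 1, symptom days 1, baseline ABSS 1, corticosteroid 1: 11 in total.

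**Interior test.** Maximise Σ₍y=1₎ xβ + Σ₍y=0₎ log(1−exp(xβ)). An interior maximum exists only if every xβ < 0 at the solution. Otherwise the valid maximum lies on the boundary, and it was found by constrained maximum likelihood, which was finite in every dataset.

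**Simulation (Python; n=420, 1:1, marginal risks set to 60%/45%).** The documents give no covariate distributions or effects, so these are assumptions.

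- Set A: walk-in 30%, age mean 45 SD 16, female 55%, education 15/50/35%, smokers 25%, symptom days uniform 1–8, ABSS mean 9 SD 3.5, corticosteroid 10%.
- Set B: walk-in 50%, age uniform 18–85, female 60%, education 30/40/30%, smokers 40%, symptom days Poisson(4) limited to 1–8, ABSS mean 8 SD 3, corticosteroid 20%.
- Log-odds at c=0.70 (per SD if continuous): ABSS 0.6; age 0.4; symptom days, recruitment, smoking and corticosteroid 0.3 each; university −0.3; secondary −0.1; sex 0.1. These were multiplied by 0.5, 0.25 and 0 for c=0.61, 0.56 and 0.50.

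Ranges cover sets A and B, and the shares also cover two runs. One run had 4,000 trials per scenario, plus 120 trials × 100 resamples for the bootstrap. The other had 300 trials × 200 resamples.

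| Assumed c | No interior maximum: trial datasets | No interior maximum: resamples | Mean RR, constrained log-binomial | Mean RR, standardised logistic | Power, constrained | Power, standardised |
|---|---|---|---|---|---|---|
| 0.50 | 6–9% | 32–40% | 0.746–0.750 | 0.748–0.751 | 77–78% | 78–79% |
| 0.56 | 23–30% | 49–58% | 0.749–0.750* | 0.747–0.750* | 77% | 78% |
| 0.61 | 65–71% | 77–85% | 0.760–0.763 | 0.748–0.751 | 74–75% | 80–81% |
| 0.70 | 99–100% | 99–100% | 0.798–0.801 | 0.748–0.751 | 61–62% | 83–85% |

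*Smaller runs with set A (300 and 400 trials).

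The true risk ratio is 0.75. Power is the share of trials in which −log RR divided by its SD across trials exceeds 2.2414. It does not reproduce the planned bootstrap with imputation.

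**Other covariate assumptions.** A separate simulation (200 trials per scenario) gave boundary shares of 11.5%, 40%, 88% and 100% at c of about 0.50, 0.57, 0.64 and 0.75. In resamples the shares were 40%, 59%, 94% and 100%.

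**True log-link model, c about 0.61.** 64–67% of trial datasets have no interior maximum, but the mean risk ratio is 0.751–0.753 against 0.749–0.751, and power is 1 point lower.

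**Unconstrained routines.** Iteratively reweighted least squares (statsmodels) gave an error, non-convergence or a fitted risk of 1 or more in 30–31%, 53–57%, 85–86% and 100% of trial datasets, from c=0.50 to 0.70. Part of this is the routine itself: at c=0.50 it also failed in 26–28% of datasets that do have an interior maximum. Newton with step-halving converged only where an interior maximum exists (agreement in 7,999 of 8,000). Elsewhere it stopped short. At c=0.61 the mean risk ratios for step-halving, constrained and standardised were 0.794, 0.759 and 0.747 (set A) and 0.790, 0.763 and 0.753 (set B).

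**Lower antibiotic use (assumed).** At 30%/22.5% the shares of trial datasets are 0.1–0.3% (c=0.50), 11–16% (0.61) and 81% (0.70). At 20%/12% they are 0.3%, 7–8% and 56–58%.

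**Recruitment type only.** 0% of trial datasets.

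**The case against.** The strongest defence is that only one word is wrong. The estimand asks for a risk ratio, the log link delivers one, and the command is offered as an example. The high boundary shares need covariate effects that the documents do not give. With non-prognostic covariates the share of trial datasets is under 10% in the main runs (11.5% in the separate simulation), and up to c=0.56 the estimates barely differ. The larger bias and power gaps arise under a logistic truth, which favours the proposed replacement; with a true log link they nearly vanish. Section 6.7 specifies Stata 18, which was not tested, and the Python failures partly reflect the routine. Antibiotic use may also fall below plan, since exclusion criterion 1 removes infections that require antibiotics, and the shares then drop.

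All of this limits the size of the effect, and it stands. It does not remove the two defects. If the command is only illustrative, the governing text is a logistic regression, which does not by itself yield the E2.1 risk ratio. Even with non-prognostic covariates, about a third or more of resamples at 60%/45% have no interior maximum, and the plan runs 1,000 resamples without saying what to do with them. Correcting the word and adding a convergence rule would be a minimal repair. Logistic regression with standardisation is preferred because it avoids the boundary altogether.

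**Conclusion.** The concern holds and should be fixed before analysis. The conflict between the named and coded models, and the absence of a rule for a failed fit, are plain from the text and need no assumptions.

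The numerical size depends on covariate effects that are not in the documents. At the planned 60%/45%, the share of trial datasets with no interior maximum runs from under 10% with non-prognostic covariates to nearly all at c=0.70. The pull of the constrained risk ratio towards 1 is about 0.01 at c=0.61 and 0.05 at c=0.70, and only if covariates act on the logit scale. It is negligible with weak covariates or a true log link.

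A materially wrong standard error under the current plan was not shown. Clustering by practice and missing data were not simulated. The sample size and the model adjusted for recruitment type alone are not affected.

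**What to change.** In Section 6.2.1, replace the command with a logistic regression on the E2.1 covariates, followed by marginal standardisation (g-computation, for example Stata margins) to the adjusted risk ratio. Run both steps inside each bootstrap resample to obtain the interval. This reconciles the named model, the promise of marginal estimates and the risk-ratio estimand. Name Poisson regression with robust standard errors as the fallback for a failed fit, and report the number of failed resamples. The per-protocol analysis inherits the change through Section 6.2.2. The resampling unit and the combination with ten imputations are separate matters.

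The cost is SAP wording and a few lines of code; n=420 is unchanged. There is no material loss of precision. At c=0.61 the mean bootstrap standard error of the log risk ratio was 0.094–0.096 for standardised logistic, 0.094–0.097 for Poisson, and 0.095–0.099 for constrained log-binomial with boundary resamples kept. At 60%/45%, logistic regression fitted in all 32,000 trial datasets and all 96,000 resamples of one run; in the other run at most 0.005% of resamples failed.
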